#### **Secondary outcomes:**

- 1. Pain Relief (PR) at 2 hours, defined as the percentage of patients having a reduction of a moderate or severe migraine headache (Grade 2 or 3) at baseline to a mild headache or to no headache (Grade 1 or 0) at 2 hours after the beginning of the e-TNS session.
- 2. Percentage of patients with absence of photophobia, phonophobia, nausea, vomiting at 2 hours after the beginning of the e-TNS session.
- 3. Use of rescue medication between 2 and 24 hours, defined as the percentage of patients who took acute anti-migraine medication between 2 and 24 hours after the beginning of the e-TNS session.
- 4. Sustained pain freedom at 24 hours, defined as the percentage of patients having no headache (Grade 0) at 2 hours, with no use of rescue medication and no relapse of headache pain within the 24 hours after the beginning of the e-TNS session.

Note: The baseline corresponds to the beginning of the e-TNS session.

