# 2. Study objective

The main objective of this study is to have a pilot assessment of the efficacy of the Cefaly® Abortive Program device used at home for 2 hours to treat a migraine attack, as triptans are generally used. That is to say having pilot data to assess the efficacy of the Cefaly® Abortive Program device in the abortive treatment of acute migraine as measured by 2-hour pain freedom, pain relief and migraine associated symptoms freedom, plus evolution of these measurements for 24 hours after the beginning of the treatment session.

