# 3. Study outcomes

# 3.1. Efficacy outcomes

#### **Primary outcomes:**

- 1. Pain Freedom (PF) at 2 hours, defined as the percentage of patients having a reduction of a moderate or severe migraine headache (Grade 2 or 3) at baseline to no headache (Grade 0) at 2 hours after the beginning of the e-TNS session.
- 2. Most bothersome migraine-associated symptom (MBS) freedom at 2 hours, defined as the percentage of patients with absence, at 2 hours after the beginning of the e-TNS session, of the most bothersome migraine-associated symptom identified at baseline.

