#### 4.2.2. Acute treatment phase

During the 2 months following the screening visit, the patient will be instructed to treat a single qualifying migraine headache. A migraine headache is a qualifying migraine if all the following conditions are met:

- 1. The migraine headache severity is moderate or severe (Grade 2 or 3).
- 2. The migraine headache is associated with at least one of these migraine-associated symptoms: photophobia, phonophobia, nausea, vomiting.
- 3. The migraine headache started less than four hours ago or the patient woke up with migraine.
- 4. No other migraine headache or headache has occurred in the previous 48 hours.
- 5. The migraine headache is not already resolving on its own i.e. the pain is not already diminishing.
- 6. No acute anti-migraine medication has been taken since the beginning of the migraine headache.

In case of qualifying migraine, patient will have to apply the Cefaly® Abortive Program device for a complete treatment session of 2 hours as soon as the migraine headache is moderate or severe (Grade 2 or 3).

In his/her diary, the patient will note the headache pain severity on the following scale: 0 = no pain; 1 = mild pain; 2 = moderate pain; 3 = severe pain. The patient will note as well the migraine associated symptoms (photophobia, phonophobia, nausea, vomiting) and will specify which associated symptom is the most bothersome symptom (MBS). The patient will note this data just before the start of the Cefaly® Abortive Program (baseline data) and 2 hours after the beginning of the treatment session (normally just after removing the device and the electrode if the session ran correctly) (2-hour data), whatever the duration of the stimulation session. The patient will also have to record if any aura was associated with the qualifying migraine attack.

Devices will be programed for only 1 treatment session to be performed at home to treat the qualifying migraine.

The Cefaly® device will be programed with the following parameters (Abortive Program): square pulse current (100 Hz,  $250 \mu s$ ) at a linearly increasing intensity starting at 0 mA up to a maximum of 16 mA after 14 minutes, then remaining stable for the rest of the session (106 minutes).

Patients will be instructed to not take any acute anti-migraine medication during the acute treatment .

phase.

During the acute treatment phase, when the Cefaly® Abortive Program device stopped, it may not be

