# 7. Practical study modalities

# 7.1. Efficacy outcome measures

The treatment efficacy outcomes will be assessed based on the following clinical data.

- **Headache pain severity.** In order to evaluate the modification of pain severity from baseline to 2-hour and 24-hour time points, patients will be asked to note their headache pain intensity on the following scale: 0 = no pain; 1 = mild pain; 2 = moderate pain; 3 = severe pain.
- **Migraine associated symptoms**. The patient will also note the presence of migraine associated symptoms (photophobia, phonophobia, nausea, vomiting) and will specify which associated symptom is the most bothersome symptom (MBS).
- **Rescue medication intake**. The patient will also record whether he/she took ANY acute rescue medication during the 24 hours following the beginning of the e-TNS session.

The following table depicts when the different measures will be made:

	At baseline, i.e. just before the beginning of the e-TNS session	2 hours after the beginning of the e-TNS session	24 hours after the beginning of the e-TNS session
Headache pain severity	•	•	•
Migraine associated symptoms	•	•	•
Most bothersome migraine associated symptom (MBS)	•		
Rescue medication intake			•

All clinical data will be collected on a paper diary and AE collecting form.

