#### 8.2.2. Statistical methods

- All relevant general, safety and efficacy data will be descriptively summarized at each time point.
- Continuous data will be summarized by the number of subjects (N), the arithmetic mean, the standard deviation, the coefficient of variation as a percentage (CV%), the median, the interquartile range, the minimum and the maximum value.
- Categorical data will be summarized by absolute (N) and relative (%) frequency tables.
- Where considered as relevant, the study data will also be graphically depicted.
- For each patient, the outcomes will be calculated according to all data available, and if necessary, imputation of missing data will be performed according to the last value carried forward method.
- Unless otherwise stated, all statistical tests will be conducted at the  $\alpha$ =0.05 (2-sided) level.

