#### 8.2.3. Statistical analysis

Modified intention-to-treat (mITT) analysis

Patient data will be included in the mITT analysis if all the four following conditions are met:

- 1. The patient treated a qualifying migraine.
- 2. The patient applied the Cefaly® Abortive Program treatment during at least one minute\*.
- 3. The headache pain severity score **AND** the migraine associated symptom(s) at baseline were reported in the diary.
- 4. The headache pain severity score **OR** the migraine associated symptom(s) at 2 hours were reported in the diary.

Data provided by Colucid Pharmaceuticals, Inc. and available on the following website: https://globenewswire.com/news-release/2016/09/06/869611/0/en/CoLucid-Pharmaceuticals-Announces-Achievement-of-Both-Primary-and-Key-Secondary-Endpoints-in-the-SAMURAI-Phase-3-Pivotal-Trial-of-Lasmiditan-in-Migraine.html (consulted in May 2017).

\*If the patient stopped the 2-hour treatment session before its end for any reason, he/she is kept in the modified intention-to-treat (mITT) analysis if all the other conditions are met.

If the patient takes rescue medication between 2 hours and 24 hours after the beginning of the e-TNS session, the headache pain intensity and associated symptoms presence can be affected by the medication and the last value carried forward method (2-hour value carried forward method in this case) will be applied for the 24-hour time point headache pain severity and migraine associated symptoms.

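### Does secondary outcome 2 need a stated form and denominator before its 2-hour symptom-absence rate can be used?

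*Combined protocol and SAP*

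**What the plan says.** The secondary outcomes in section 3.1 of the combined protocol and SAP include "Percentage of patients with absence of photophobia, phonophobia, nausea, vomiting at 2 hours after the beginning of the e-TNS session". The four symptoms stand in a bare list under one percentage. No word says whether they are taken jointly or one at a time, and baseline status is not mentioned. The neighbouring outcomes do refer to baseline: pain freedom and pain relief start from Grade 2 or 3, and the second primary outcome concerns the absence "of the most bothersome migraine-associated symptom identified at baseline".

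The objective in section 2 names "2-hour pain freedom, pain relief and migraine associated symptoms freedom" as the 2-hour measures, so symptom freedom appears there as a single item.

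The only analysis set is mITT. Section 8.2.3 opens its definition with "Patient data will be included in the mITT analysis if all the four following conditions are met". The first condition is "The patient treated a qualifying migraine", and section 4.2.2 requires such an attack to be "associated with at least one of these migraine-associated symptoms: photophobia, phonophobia, nausea, vomiting". The third condition requires baseline symptoms to be in the diary. The fourth is met by either a pain score or symptoms at 2 hours.

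On reporting, section 8.2.2 states: "All relevant general, safety and efficacy data will be descriptively summarized at each time point". It prescribes counts and percentages for categorical data and last value carried forward for missing data. The table in section 7.1 schedules the symptoms at baseline, 2 hours and 24 hours.

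**The concern.** Two analysts could take the same sentence and report different quantities: one composite rate, or four separate rates.

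One symptom is enough for an attack to qualify, so a patient may enter with photophobia and no vomiting. If vomiting is reported on its own over all mITT patients, that patient is free of vomiting at 2 hours without anything having resolved. Read as symptom freedom, the rate then mixes resolution with absence from the start, and more so for rarer symptoms. A randomised comparison would carry the same baseline absence in both arms, but this open-label study has no comparator group.

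Last value carried forward adds to this. A patient can enter mITT with only a pain score at 2 hours, and a symptom absent at baseline would then be carried forward as absent.

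At stake is how one secondary result is read, and possibly carried into the randomised trial that section 1 says this pilot is meant to prepare.

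**Working it through.** The plan gives no expected value for this outcome, so there is no figure of its own to reproduce. The inputs are the mITT conditions (section 8.2.3), the qualifying-attack rule (section 4.2.2), the reporting rules (section 8.2.2) and the 42 patients of the power statement (section 8.2.1), used only to give the examples a scale. Symptom prevalence and resolution rates are not in the documents and are assumed below.

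**All-four reading.** mITT requires a qualifying attack, and a qualifying attack requires at least one of the four symptoms. The share of mITT patients free of all four at baseline is therefore 0%, so nobody is a success on baseline absence alone. A patient whose 2-hour symptoms are missing has at least one symptom carried forward as present and counts as a failure. This reading has no inflation to correct.

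**Per-symptom reading over all mITT patients.** Let b be the baseline prevalence of a symptom and f the proportion of affected patients in whom it is gone at 2 hours, with no new onset.

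- Reported absence rate = (1 − b) + b·f
- Excess over f = (1 − b)(1 − f)

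| Assumed b | Rate if f = 0 | Rate if f = 30% | Excess over 30% |
|---|---|---|---|
| 90% | 10% | 0.10 + 0.27 = 37% | 0.10 × 0.70 = 7 points |
| 50% | 50% | 0.50 + 0.15 = 65% | 0.50 × 0.70 = 35 points |
| 10% | 90% | 0.90 + 0.03 = 93% | 0.90 × 0.70 = 63 points |

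The excess can be large, but these values only show how it behaves. They do not estimate it for this trial.

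**What the planned tables would show.** Suppose that, of 42 patients, 21 have the symptom at baseline and 15 have it at 2 hours (assumed counts).

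- Absent at 2 hours: (42 − 15)/42 = 27/42 = 64%.
- Absent at baseline: (42 − 21)/42 = 21/42 = 50%.
- Net change among those affected at baseline: (21 − 15)/21 = 6/21 = 29%.

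Section 8.2.2 calls for summaries at each time point, so the 50% would be reported as well as the 64%. A reader can see that most of the 64% was there at the start.

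**What the tables would not show.** With k new onsets, the number resolved is 6 + k. This gives 6/21 = 29%, 7/21 = 33% and 8/21 = 38% for k = 0, 1 and 2, and the two marginal counts are the same in all three cases. The remaining ambiguity in this example is 29% against 33% or 38%. The Wilson 95% interval for 6/21 is 14% to 50%, so sampling error is larger than that difference.

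**Cost of a restricted denominator.** For a symptom with 10% prevalence, 0.10 × 42 = 4.2, or about 4 patients. A result of 1/4 has a Wilson 95% interval of 5% to 70%. Where the inflation is largest, the restricted rate says least.

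**The case for a change.** The strongest case for a change is that the definition really is incomplete. The objective leans towards the composite without fixing it. If the form is chosen after the data are seen, there is some freedom to report the more favourable version. Marginal frequencies give net change and not resolution. The neighbouring outcomes are conditioned on baseline and this one is not. A clarifying sentence would cost nothing, because the data are already collected.

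Part of this stands. The sentence can be read two ways, the planned tables cannot separate resolution from new onset, and a report should say which form it gives and over which patients. Carrying forward a baseline absence as a 2-hour absence is also a real feature of the per-symptom form when 2-hour symptoms are missing.

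The rest does not make the plan wrong. The composite is sound as it stands. The per-symptom rate is a true statement about status at 2 hours, and it misleads only a reader who takes it for resolution without looking at the baseline row. No test, threshold or decision is attached to this outcome, so the freedom to choose a form affects its description only. The restricted rate has its own limits: it leaves out patients who develop the symptom by 2 hours, and it still includes natural resolution, so it would not isolate a device effect either.

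**Conclusion.** No change to the plan is needed. Secondary outcome 2 lacks a stated form and denominator. Under one reading the result is free of the problem, and under the other it is a valid description reported together with its baseline counterpart. Following the plan as written gives no wrong number and supports no wrong conclusion.

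The size of the possible inflation cannot be drawn from the documents; the 7, 35 and 63 points rest entirely on assumed prevalence and an assumed 30% resolution. The primary outcomes and the sample size are untouched. Because baseline symptoms are a condition of entering mITT, an analyst can produce the composite, or a per-symptom rate among patients affected at baseline, without new data, and can label it in the report.

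This conclusion assumes that the qualifying-attack rule is applied when patients are admitted to mITT, and that the baseline frequencies are reported as section 8.2.2 provides.

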4.2.3. Post-treatment phase

Two hours after the beginning of the treatment session, the patient is allowed to take rescue medication

if the migraine headache pain is still moderate or severe, or if after initial pain relief (no headache or

mild headache pain) a moderate or severe headache is resuming.

The patient will have to note the headache pain severity in his/her diary at 24 hours after the beginning

of the treatment session (24-hour data), as well as the migraine associated symptoms. Patients will also

be instructed to record in their diary the rescue medication intake, if any, during the 24 hours following

the beginning of the treatment session.

In his/her AE collecting form, the patient will record any adverse event occurring during the 24 hours

following the beginning of the treatment and is instructed to notify the investigator immediately for any

serious or severe adverse experience with the stimulation.

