4.2.4. Final visit

The patient will be instructed to return to the study site within approximately 4 days after the treatment

session to return the study material as well as completed diary and AE collecting form. The investigator

will review the paper diary in detail to ensure data accuracy (to avoid any missing data, unclear data

or discrepancies). If necessary, the investigator will instruct the patient to make him/herself corrections

and to sign the corrections with his/her screening number and the date (no initials).

All adverse events reported on the AE collecting form will be reviewed by the investigator to assess

severity. Additionally, the investigator will ask the patient if he/she has experienced any adverse effect

not reported on the form.

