#### 9.5. AE collection

The patients are instructed to report all AEs to the investigator during the 2 hours of the protocol. AEs will be analyzed by the investigator who will document it in the CRF.

All AEs will be collected in the CRF, specifying:

- Their nature
- Start date and duration
- Causality (according to investigator's opinion)
- Countermeasures and results

If the AE is a SAE, the promoter should be notified as soon as possible.

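### Sustained pain freedom requires no relapse over 24 hours, but the listed data miss an untreated relapse that resolves before then, so the reported rate can be too high

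*Combined protocol and SAP*

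**What the plan says.** Section 3.1 defines sustained pain freedom at 24 hours by a 2-hour grade of 0 together with this condition: "with no use of rescue medication and no relapse of headache pain within the 24 hours after the beginning of the e-TNS session". It gives no grade at which a returning headache counts as relapse.

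Section 7.1 lists the clinical data on which efficacy will be assessed. Pain is graded 0 to 3, with this stated purpose: "In order to evaluate the modification of pain severity from baseline to 2-hour and 24-hour time points". The table in 7.1 schedules pain severity at those three times and no others. The patient also records "whether he/she took ANY acute rescue medication during the 24 hours following the beginning of the e-TNS session".

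Section 4.2.3 describes the same single later pain entry: "The patient will have to note the headache pain severity in his/her diary at 24 hours after the beginning" of the session. It permits rescue medication from 2 hours onward if pain is still moderate or severe, or becomes so again after initial relief. Section 6.5 likewise ties rescue to Grade 2 or 3 pain.

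**The concern.** Absence of relapse is a condition on the whole period from 2 to 24 hours. Pain is measured only at the two ends of that period, and the one efficacy item that covers the time between is rescue intake. The outcome therefore depends on something the listed data only partly observe.

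The gap can arise in a patient who follows every instruction. Rescue is permitted only for moderate or severe pain, so a mild recurrence managed as instructed goes untreated. If it clears before 24 hours, the record is Grade 0, Grade 0 and no rescue.

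A missed relapse can only turn a failure into a success, so the bias has one direction. The course of symptoms over 24 hours is part of the objective in section 2. Section 1 says the pilot is to supply data for a later controlled trial, so an inflated durability rate, and a diary that cannot verify it, could be carried into that trial.

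**Working it through.** **Which relapses the plan catches.** For a patient at Grade 0 at 2 hours whose headache returns:

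| Course after 2 hours | Trace in the 7.1 data | Scored as |
|---|---|---|
| Rescue taken | Rescue intake | Not sustained (correct) |
| No rescue, pain present at 24 hours | 24-hour grade above 0 | Not sustained (correct) |
| No rescue, pain gone by 24 hours | None | Sustained (wrong) |

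**Inputs.** The plan states no figure for sustained pain freedom or relapse, so there is none to reproduce. Section 8.2.1 supplies the base: 42 evaluable patients (42 / (1 − 0.30) = 60 to be included) and 32.2% expected pain-free at 2 hours. That is 42 × 0.322 = 13.5 patients.

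Two quantities have to be assumed, because the documents do not give them:
- R, the share of patients pain-free at 2 hours who relapse by 24 hours;
- U, the share of those relapses that are untreated and resolved by 24 hours.

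**Formulas**, with every other relapse taken as caught:
- true rate = 32.2% × (1 − R)
- reported rate = 32.2% × (1 − R × (1 − U))
- overstatement = 32.2% × R × U

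| R | U | Reported | True | Overstatement | Patients of 42 |
|---|---|---|---|---|---|
| 10% | 10% | 29.30% | 28.98% | 0.32 points | 0.14 |
| 25% | 30% | 26.57% | 24.15% | 2.42 points | 1.0 |
| 40% | 50% | 25.76% | 19.32% | 6.44 points | 2.7 |
| any | 0% | equals true | 32.2% × (1 − R) | 0 | 0 |

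One misclassified patient is worth 1/42 = 2.4 points. For one to be expected, R × U must reach 1/13.5 = 7.4%.

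**A related rule.** Section 8.2.2 fills missing values by last value carried forward. A missing 24-hour grade after Grade 0 at 2 hours would become Grade 0, which pushes the rate the same way. The carry-forward after rescue in 8.2.3 does no harm here as long as the no-rescue condition is applied separately.

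**The case against.** - **The threshold is not stated.** Section 3.1 gives no grade for relapse, and 4.2.3 speaks of moderate or severe headache returning. If only Grade 2 or 3 counts, the mild, compliant case is not a relapse. This narrows the gap without closing it: rescue is permitted, not required, so a moderate or severe recurrence can also go untreated and clear. It is a further reason to define the term.
- **The diary form is not in the documents.** It may contain a relapse item, and this cannot be excluded. But 7.1 sets out the data on which efficacy will be assessed, and no such item is there.
- **Other sources could reveal a relapse.** Section 4.2.3 has adverse events recorded for 24 hours, 9.4 lists headache after the session as an expected event, and at the final visit (4.2.4) the investigator reviews the diary and asks about unreported effects. However, no rule carries any of this into outcome 4, and a diary reading Grade 0, Grade 0, no rescue shows no discrepancy to query. Section 9.5 states a shorter window: "The patients are instructed to report all AEs to the investigator during the 2 hours of the protocol". That conflicts with 4.2.3 and needs reconciling, but it does not prove that 24-hour adverse event data will be absent.
- **The stakes are modest.** This is a single-arm, open-label pilot, and the outcome is one of four secondary ones with no stated test or threshold. The objective in section 2 asks how the measurements evolve over 24 hours, which the 24-hour rating partly serves. R, U and the 32.2% base are all assumed or borrowed. These points stand, and they limit how much weight the concern deserves.

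**Conclusion.** The concern holds. As written, the plan scores an untreated relapse that resolves before 24 hours as sustained pain freedom, and the resulting error can only be upward. This follows from setting 3.1 against 7.1 and 4.2.3, and does not depend on the assumed rates.

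The size is unknown. The illustrations run from 0.3 to 6.4 points, with 2.4 points (about one patient) in the middle case, and the overstatement is zero if no relapse is both untreated and resolved. They rest on assumed R and U, on 32.2% being pain-free at 2 hours, and on complete data. The conclusion also assumes that the diary holds no relapse item beyond those described.

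Both primary outcomes are assessed at 2 hours and are untouched. This is a worthwhile, cheap correction to one secondary outcome, not a threat to the study.

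**What to change.** Add one item to the 24-hour diary entry: *Did any headache return between 2 and 24 hours? If so, when, and what was its worst grade (1 to 3)?* Add the matching row to the table in 7.1, and state in secondary outcome 4 that a positive answer counts as relapse. This makes the any-grade reading explicit. If a higher threshold is meant, 3.1 should say so, and the worst-grade entry allows it to be scored. If the diary already has such an item, listing it in 7.1 with the scoring rule is enough.

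The cost is one question on a paper form and one table row. The drawbacks are some recall error and a possibly lower reported rate. Treatment and rescue rules are not touched.

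If the diary cannot be changed, redefine the outcome as Grade 0 at both 2 and 24 hours with no rescue medication, drop the no-relapse condition, and require an observed 24-hour grade rather than one carried forward. With complete 24-hour data this leaves the reported number as it is, but the claim then matches what was measured.
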